Safety Evaluations	Periodic review will be performed by the NC TraCS DSMB. They will review aggregate safety data after 25, 50, and 75% enrollment to ensure there are not safety differences between the groups in hypotension requiring vasopressors and development of pneumothorax. All patients will have

continuous monitoring of HR, BP, and oxygenation per ICU protocol to monitor patient safety.

Statistical And Analytic Plan

This is a randomized, controlled trial to evaluate the effect of using Optimal PEEP based on an esophageal balloon measurement on duration of mechanical ventilation. We hypothesize that using Ptp to identify optimal PEEP will reduce time on the ventilator and therefore increase the ventilator free days at day 28. The primary outcome is the number of ventilator-free days, defined as the number of days alive and ventilator-free by day 28. Differences between the two groups in the primary outcome will be analyzed using independent t-tests and a linear regression model adjusting for BMI, abdominal girth, and Ptp.

DATA AND SAFETY MONITORING PLAN

The PI will be responsible for maintaining patient data and ensuring accuracy of the data collected. All patient data will be collected using REDCap through the NC TraCS system. REDCap allows for immediate data validation and range setting to reduce the likelihood of erroneous data entry. Data created for analysis will be de-identified and secured on a password protected UNC School of Medicine network hard drive. All investigators will be trained on completing the electronic case report form.

Patient safety will be monitored with continuous cardiovascular monitoring by the critical care team. Subject stopping rules will be in place to end the study intervention, including refractory hypotension, development of pneumothorax, or changes in oxygenation or hemodynamics that the primary team feels may be related to changes in PEEP.

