3.4 Study Population

Inclusion Criteria: Obese adults (BMI ≥ 40) admitted to the MICU at UNC Hospital or the ICU at Vidant Medical Center ECU with acute respiratory failure requiring mechanical ventilation.

Exclusion Criteria:

1. Refusal to give consent by the subject or their LAR
2. Abdominal compartment syndrome
3. Chest tube for pneumothorax
4. Having been on a ventilator for >4 days
5. Suspicion of or known intracranial hypertension
6. Anticipated extubation within 24 hours
7. Chronic ventilator dependence
8. Condition that precludes placement of an esophageal balloon (esophageal or nasopharyngeal pathology preventing insertion of the esophageal balloon catheter, severe thrombocytopenia or coagulopathy)
9. Incarceration
10. Not expected to survive >48 hours
11. Unable to obtain consent from subject or LAR
12. Unable to obtain consent due to a language barrier

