5.2 Other measurements

Variable	Source	How Measured	Baseline	Daily	Completion
Outcomes					
Ventilator free days at day 28 (Primary outcome)	EMR	Days alive and free of the ventilator			X
Reintubation	EMR	Intubated within 72 hours of extubation		X	X
ICU Length of Stay	EMR	Days			X
Hospital Length of Stay	EMR	Days			X
Tracheostomy	EMR	Y/N			X
Extubation prior to meeting established criteria	EMR	Y/N			X
Highest RASS	EMR	-5 to +4 (single highest value used)	X	X	
Lowest RASS	EMR	-5 to +4 (single lowest value used)	X	X	
Exposures					
Esophageal pressure (Pes)	Ventilator	cm H ₂ O	X	X	
Airway pressure (Paw)	Ventilator	cm H ₂ O	X	X	
Transpulmonary pressure (Ptp) (inspiratory and expiratory)	Ventilator	cm H ₂ O	X	X	
PEEP	Ventilator	cm H ₂ O	X	X	
Opioids	EMR	Continuous, bolus sch, bolus prn, oral sch, oral prn	X	X	
Propofol	EMR	Y/N	X	X	
Dexmedetomidine	EMR	Y/N	X	X	
Benzodiazepines	EMR	Continuous, bolus sch, bolus prn, oral sch, oral prn	X	X	
Antipsychotics	EMR	Sched, PRN	X	X	
Neuromuscular blockade	EMR	Y/N	X	X	
Corticosteroid use	EMR	Y/N	X	X	
Fluid Balance	EMR	Net fluid balance prior to extubation		X	
Safety Measures					
Vasopressor requirement	EMR	norepinephrine equivalents(9)	X	X	
Pneumothorax	EMR	Y/N	X	X	
Other Variables of Interest					
Age	EMR	Years	X		
Race/Ethnicity					
BMI	EMR	kg/m ²	X		
Partial Pressure of Oxygen (PaO ₂)	EMR	mmHg	X	X	
Oxygen Saturation (SpO ₂)	EMR	%	X	X	

PaO ₂ /FiO ₂ ratio	Calculated	Number	X	X	
SpO ₂ /FiO ₂ ratio	Calculated	Number	X	X	
Charlson Comorbidities	EMR	Y/N	X		
Waist circumference	EMR	cm	X		
CAM-ICU	EMR	Positive/Negative	X	X	
SOFA	EMR	Calculated	X		
COVID (y/n)	EMR	Y/N	X		

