6.2 Statistical Methods

All continuous variables (see 5.2) will be described using mean and standard deviation, with associated 95% confidence intervals, or median with interquartile range as appropriate based on normality of distribution. All categorical variables will be described with frequency and percentage.

To determine if the optimal PEEP has an effect on the duration of mechanical ventilation compared to usual PEEP, the primary outcome will be analyzed with a 2-sided independent t-test. As secondary analysis, the associations between the primary outcome and exposures and demographic variables will be further analyzed using linear regression models.

The impact of optimal PEEP vs standardized PEEP titration will be assessed on all other variables with independent t-tests or chi-square tests as appropriate. All secondary outcomes, as described in 5.2, will be further analyzed with either linear regression models or logistic models, using demographic and exposure variables as predictors.

All tests will be 2-sided, and p-values < 0.05 will be considered significant. Tests with p-values above 0.05 will be considered inconclusive. Missing values will be ignored.

No interim analyses for efficacy or futility are planned, but interim analyses will be conducted for safety.

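### The primary comparison of ventilator-free days is unadjusted and no planned model names the baseline prognostic measures already collected; a short, fixed baseline-adjusted model would probably be more precise at little cost

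*Combined protocol and SAP*

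**What the plan says.** Section 6.2 states that "the primary outcome will be analyzed with a 2-sided independent t-test". Regression comes second: "the associations between the primary outcome and exposures and demographic variables will be further analyzed using linear regression models". The models for secondary outcomes are described in the same terms, "using demographic and exposure variables as predictors". Section 6.2 lists no covariate by name.

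The synopsis (Statistical And Analytic Plan) describes the analysis of the primary outcome differently, as "independent t-tests and a linear regression model adjusting for BMI, abdominal girth, and Ptp", and does not say which of the two carries the conclusion.

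The table in Section 5.2 has a group for exposures and a separate group headed "Other Variables of Interest". SOFA, SpO2/FiO2, PaO2/FiO2, COVID status and "Charlson Comorbidities" are in the second group, all marked for collection at baseline. The exposures group holds Pes, Paw, Ptp, PEEP, sedatives, neuromuscular blockade, corticosteroids and fluid balance. All are recorded daily, and all but fluid balance at baseline as well.

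Exclusion 4 in Section 3.4 is "Having been on a ventilator for >4 days", so screening must establish time already ventilated. The Section 5.2 table does not list it as a variable.

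**The concern.** In a randomised trial of 38 per arm, baseline variables that predict the outcome can be used to shrink the residual variance of the treatment comparison. Acute severity, oxygenation and COVID status are natural candidates for predicting days alive and off the ventilator. The plan collects them and then names none of them in any model. The covariates it does name look less promising: BMI is restricted by eligibility to 40 or more, and girth can be expected to overlap with BMI.

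There is a second, related weakness. The models in Section 6.2 draw on exposures, most of which are measured both at baseline and daily after randomisation, and neither Section 6.2 nor the synopsis restricts the models to baseline values. PEEP is what the intervention changes, and Ptp is what it targets. Using their post-randomisation values as covariates in a treatment-effect model could remove part of the effect under study.

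At stake are precision in a trial sized at 80% power for a 2-day difference, whose Section 6.3 itself anticipates that the effect may be smaller, and a covariate set that could be settled after the data are seen.

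**Working it through.** **Inputs.** From Section 6.3: SD 2.9 days (for duration of ventilation, carried over to VFD), difference 2 days, 80% power, alpha 0.05, 34 per group, 10% dropout, 38 per group. From Section 6.2: two-sided test. Assumed: R2, the share of VFD variance explained by the baseline covariates. The documents give no value, so 0.05 to 0.30 is shown.

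**The plan's own figures.** A two-sample t-test for 2 days with SD 2.9 needs 33.99, so 34 per group. For 3 days it needs 15.69, so 16 per group. Allowing for dropout, 68/(1 − 0.10) = 75.6, so 76. All three agree with Section 6.3. Power at 34 per group is 80.0%:

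- SE = 2.9 × √(2/34) = 0.703 days
- noncentrality = 2/0.703 = 2.84 on 66 df

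**With adjustment.** Take k = 4 covariates (SOFA, SpO2/FiO2, COVID, prior ventilator days), so df = 68 − 2 − 4 = 62. The residual SD is 2.9 × √(1 − R2). Chance correlation between covariates and arm inflates the variance by about 66/62, so

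SE = 2.9 × √(1 − R2) × √(2/34) × √(66/62), where √(66/62) = 1.032.

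Power follows from the noncentral t distribution on 62 df with noncentrality 2/SE.

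| R2 (assumed) | Residual SD | SE (days) | SE against unadjusted | Power |
|---|---|---|---|---|
| Unadjusted test | 2.900 | 0.703 | – | 80.0% |
| 0.05 | 2.827 | 0.707 | +1% | 79.5% |
| 0.10 | 2.751 | 0.688 | −2% | 81.6% |
| 0.20 | 2.594 | 0.649 | −8% | 85.8% |
| 0.30 | 2.426 | 0.607 | −14% | 90.0% |

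The standard error breaks even where (1 − R2) × 66/62 = 1, that is R2 = 4/66 = 0.06.

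**How far chance imbalance could move the estimate.** With 38 per arm, the shift in the mean difference due to covariate imbalance has standard deviation √R2 × 2.9 × √(2/38):

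- R2 = 0.10: 0.21 days, 95% limits ±0.41
- R2 = 0.20: 0.30 days, 95% limits ±0.58
- R2 = 0.30: 0.36 days, 95% limits ±0.71

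At R2 = 0.30, a 2-day shift would be 2/0.364 = 5.5 standard deviations away.

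**The case against.** The strongest reply is that nothing is broken. An unadjusted t-test is a valid analysis of a 1:1 randomised trial, it is the method behind the sample size, and it delivers the stated power on the plan's inputs. Adjusted regressions are already planned as secondary analyses. The gain depends on an R2 that the documents do not supply, and with weak covariates it is nil or slightly negative. All of this stands, and it sets the weight of the point.

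Three stronger readings are tempting and should not be drawn.

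- A reader might infer that no planned model contains illness severity. The documents do not go that far. Demographic variables are undefined, Section 5.2 has no group of that name, and age, race/ethnicity and BMI share a block with SOFA, Charlson and COVID. Some baseline exposures, such as PEEP or neuromuscular blockade, may also track respiratory severity. What can be said is that no model names these measures and the covariate list is open.
- A reader might infer that imbalance in severity or COVID could shift mean VFD by as much as the effect sought. On the plan's SD it could not: the limits above stay within about 0.7 days.
- A reader might quote power of 84%, 88% and 92% for R2 of 0.10, 0.20 and 0.30. Those figures come from shrinking the SD without charging for the covariates.

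Charlson and COVID are, moreover, comorbidity and aetiology, not acute severity, though both remain reasonable baseline candidates.

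**Conclusion.** The point holds as a recommendation on efficiency and prespecification. The primary test ignores baseline prognostic information that the trial already collects, the planned regressions neither name that information nor exclude post-randomisation values, and the synopsis and Section 6.2 describe different models.

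The benefit is modest and conditional. Power rises by about 2, 6 and 10 percentage points at R2 of 0.10, 0.20 and 0.30, and there is no net gain at about 0.05 or less. The absolute power figures also rest on the 2.9-day SD, which describes duration of ventilation and not VFD with deaths counted. The relative change in standard error does not depend on that SD.

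**What to change.** In Section 6.2, define the primary estimate as the arm coefficient, with its 95% confidence interval, from a linear model of VFD on arm plus a short fixed list of values taken before randomisation: SOFA, SpO2/FiO2 and COVID status. SpO2/FiO2 is preferable to PaO2/FiO2 because Section 5.1 treats an arterial gas as something that may not be available. Days ventilated before enrolment can be added as a fourth covariate if it is entered in the Section 5.2 table.

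Keep the unadjusted t-test as a sensitivity analysis. Bring the synopsis into line, so that one analysis is named as primary in both places. State that no exposure measured after randomisation enters a treatment-effect model. Any model of post-randomisation exposures should be labelled as an exploratory association. The list must be fixed before outcome data are seen.

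The cost is a paragraph of wording and at most one extra field from the medical record, with no added procedure for patients. Statistically it costs up to four degrees of freedom and about 3% on the standard error before any gain from the covariates.

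### Section 6.2 tests the effect of PEEP strategy on all 33 non-primary variables, including baseline and fixed ones, and calls each p < 0.05 significant without multiplicity control or an exploratory label

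*Combined protocol and SAP*

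**What the plan says.** Section 6.2 (Statistical Methods) names one primary test, a two-sided t-test on ventilator-free days. For everything else it says: "The impact of optimal PEEP vs standardized PEEP titration will be assessed on all other variables with independent t-tests or chi-square tests as appropriate".

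The decision rule is common to all tests: "All tests will be 2-sided, and p-values < 0.05 will be considered significant", and "Tests with p-values above 0.05 will be considered inconclusive". Section 6.2 states no hierarchy, no multiplicity adjustment and no exploratory label.

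The variables are those of the table in Section 5.2, to which Section 6.2 points when it describes the summaries: "All continuous variables (see 5.2) will be described using mean and standard deviation". The table has four blocks: outcomes (headed by the primary, "Ventilator free days at day 28"), exposures, safety measures, and "Other Variables of Interest". The last block includes age, "Race/Ethnicity", BMI, "Charlson Comorbidities", waist circumference, SOFA and COVID status. Six of those seven are marked for collection at baseline only. Race/ethnicity has no time point marked.

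The sentence after the testing sentence adds regression models for the secondary outcomes, with demographic and exposure variables as predictors.

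**The concern.** There are two problems, and the first needs no arithmetic.

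**Kind.** A between-arm test asks whether the assigned strategy changed the variable. Age, race, BMI, comorbidities, waist circumference, baseline SOFA and COVID status cannot be changed by a strategy assigned afterwards. With allocation concealed through REDCap (Section 4.2), a difference in any of them is the play of chance, yet the stated rule would call it a significant impact of PEEP. Pes, Paw, Ptp and PEEP raise a different difficulty. The intervention arm's PEEP is set from Ptp, which is Paw minus Pes (Section 5.1). A difference there shows that the two arms were managed differently, not that patients benefited.

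**Number.** The remaining rows are each tested at 0.05 and each may be declared significant. In a 76-patient trial whose results are meant for journals and further grant applications (Section 11), a chance secondary result could be reported as an established effect.

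**Working it through.** **1. The plan's own figures.** The documents give no family-wise error rate, so there is none to reproduce. The alpha of 0.05 in Section 6.3 belongs to the primary comparison. With a 2-day difference, SD 2.9 and 80% power, a t-based calculation gives 34 per group (power 0.800), and 68/(1 − 0.10) = 75.6, rounded up to 76. Both match Section 6.3. Nothing below changes them.

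**2. Row count (table in Section 5.2).**

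| Block | Rows | Non-primary |
|---|---|---|
| Outcomes | 8 | 7 |
| Exposures | 12 | 12 |
| Safety measures | 2 | 2 |
| Other variables | 12 | 12 |
| Total | 34 | 33 |

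Baseline or fixed: age, race/ethnicity, BMI, Charlson, waist circumference, SOFA, COVID = 7. Pressure rows: Pes, Paw, Ptp, PEEP = 4. Rows left after removing both: 33 − 7 − 4 = 22 (7 outcomes, 8 exposures, 2 safety, 5 other).

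**3. Chance of at least one false positive.** Take one test per row, all nulls true and tests independent. The chance is 1 − 0.95^k, and the expected number of false positives is 0.05 × k.

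| Set of tests | k | Chance of at least one | Expected number |
|---|---|---|---|
| All non-primary rows | 33 | 0.816 | 1.65 |
| Without the pressure rows | 29 | 0.774 | 1.45 |
| Without pressure, baseline and fixed rows | 22 | 0.676 | 1.10 |
| Outcomes and safety rows | 9 | 0.370 | 0.45 |
| Non-primary outcomes only | 7 | 0.302 | 0.35 |
| Baseline and fixed rows only | 7 | 0.302 | 0.35 |

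**4. Sensitivity to correlation.** The documents give no correlations, so these values are assumed. Simulating 33 equally correlated two-sided tests (200,000 runs) gives:

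| Correlation | 0.1 | 0.3 | 0.5 | 0.7 |
|---|---|---|---|---|
| Chance of at least one | 79.8% | 69.0% | 52.8% | 35.2% |

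**5. What could raise the figure.** Rows could be split (inspiratory and expiratory Ptp, drug routes, individual comorbidities), daily values could be tested one by one, and the regression models add further tests. The documents do not say how many tests these would make, so they are not counted.

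**The case against.** Several points on the other side are fair.

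- **The plan does identify its secondary outcomes.** A reader might infer that they are lost among the other variables. They are not: the Section 5.2 table has an outcomes block, and Section 6.2 refers to the secondary outcomes of that table and gives demographics and exposures a predictor role. What stands is narrower: the t-test and chi-square sentence ignores these groupings. Reading that sentence as limited to secondary outcomes does not fit, because the next sentence uses a separate term for them.
- **The 82% is an upper figure for 33 tests.** A reader might infer that a false positive is close to certain. The documents do not support that. Even under independence, about 1 chance in 5 of no false positive remains, and about 59 independent tests would be needed to reach 95%. Related rows (PaO₂, SpO₂ and their FiO₂ ratios; the pressures; ICU and hospital stay) tend to lower the figure. For PEEP and Ptp a true difference is intended, so a significant result there need not be false.
- **The main result is not exposed.** A reader might take the inflated error to apply to the trial's conclusion. There is one primary outcome, one prespecified test and no interim efficacy analysis, so its 5% error stands.
- **Covariate choice.** A reader might infer that baseline p-values will steer the adjustment models. Nothing in the documents says so, and the synopsis names BMI, abdominal girth and Ptp for the primary model.
- **Calling p-values above 0.05 inconclusive is sound practice.** It guards against reading non-significance as no effect, but does nothing about chance results below 0.05.

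**Conclusion.** The point holds. As written, Section 6.2 would label chance differences in seven baseline or fixed variables as significant effects of PEEP strategy, would treat four measures of treatment delivery like outcomes, and puts no control or caveat on the rest.

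The size is up to about 82% for at least one false positive over 33 rows, about 68% over the 22 rows that are neither baseline, fixed nor pressure measures, and 30% over the seven non-primary outcomes. The last figure is the most relevant to misleading secondary efficacy claims. All three assume one test per row, every null true and independent tests, and positive correlation lowers them. The fault in testing baseline and fixed variables does not depend on these figures. The primary analysis and the sample size are untouched.

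**What to change.** Replace the testing sentence in Section 6.2 so that:

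1. Baseline and fixed variables are tabulated by arm, without tests.
2. Pes, Paw, Ptp and PEEP are reported as treatment separation.
3. Treatment comparisons are limited to the post-randomisation outcome rows and the safety rows of the Section 5.2 table. Other post-randomisation rows are described by arm.
4. All non-primary comparisons are given as estimates with 95% confidence intervals, labelled exploratory and unadjusted, with no claim of a significant effect. The 0.05 rule is restricted to the primary test.

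If the sponsor wants confirmatory secondary claims, Holm adjustment over the seven non-primary outcome rows is an optional alternative (smallest p-value compared with 0.05/7 = 0.0071). Safety comparisons should stay unadjusted in either case, so that signals are not suppressed.

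The cost is SAP wording only, with no new data, patients or change to the sample size. The downside is that fewer results may be called significant.

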- 5) Other signs of respiratory distress (distress = 2 or more)
- 6) HR > 140
- 7) Marked accessory muscle use
- 8) Abdominal paradox (belly breathing)
- 9) Diaphoresis

Failure of an SBT will be determined by the bedside RT based on current policy (PolicyStat ID: 4745433). If a patient fails an SBT, they will be returned to their previous ventilator settings until the next daily assessment. If the patient tolerates a 30-minute SBT, they will be returned to their previous ventilator settings for 60 minutes, then extubated to an appropriate oxygen delivery device. Ventilator settings during the SBT and extubation procedures will vary between groups as below. Blinding of the respiratory therapist determining eligibility for SBT to treatment arm will not be possible because of the differences between SBT protocols. However, the study team will make no determinations of readiness for extubation. If a member of the study team is on service during the time of potential enrollment, these patients will be excluded to avoid bias.

SBT and Extubation Procedure for Intervention Group

Patients in the Intervention group will undergo an SBT regardless of their PEEP level. The PEEP that generates a Ptp of 0 will be considered their optimal PEEP, and this will not be lowered for the SBT. The Intervention Group SBT will consist of a trial of a pressure support of 5 cm H₂O and Optimal PEEP.

SBT and Extubation Procedure for Control Group

Patients in the Control group will undergo an SBT **when they reach a PEEP \leq 8 cm H₂O**. This is the current standard of care based on the SBT protocol at UNC Hospitals. SBT and extubation prior to meeting these criteria will be based on primary medical team's discretion and will be recorded for analysis and safety tracking.

Procedures for ventilator weaning after tracheostomy

Any patient who fails to be eligible for extubation or fails extubation will be eligible for tracheostomy per usual unit protocol. The study team will play no part in the decision to proceed with tracheostomy for ventilator weaning. After tracheostomy, it is routine practice to forego SBT and proceed with trials of liberation from the ventilator with oxygen delivered by an aerosol tracheostomy collar ("trach collar trials" or TCT). The same criteria are used to perform a TCT as an SBT above. The two groups will have different approaches to TCT.

TCT Procedure common to both groups

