6 STATISTICAL CONSIDERATION

6.1 Primary Endpoint

The primary outcome is the number of ventilator-free days (VFD), defined as the number of days alive and ventilator-free by day 28. The assessment of the primary outcome will be conducted by a study team member after subject completion in the study. In order to minimize potential bias, this team member will be blinded to treatment arm assignment.

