6.3 Sample Size and Power

We utilized preliminary data from earlier studies of mechanical ventilation in the obese to establish a baseline. With a mean duration of mechanical ventilation of 7 days with a standard deviation of 2.9 days, we expect the control group to have 21 ventilator free days. We estimate that we could reasonably see an effect in the intervention group that reduces the duration of mechanical ventilation by 3 days. With a power of 80% and alpha=0.05, we would need 16 patients per group, for a total of 32 patients. Would the effect be only a reduction of mechanical ventilation by 2 days, we would need 34 patients in each group for a total of 68 patients. Because the population in our study would be expected to have a lower mean duration of mechanical

ventilation, we anticipate we may find a smaller effect size. Including a possible 10% dropout, we will target a sample size of 76 (38 per group) to safely achieve our goals.

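### Section 6.2 admits net fluid balance before extubation as a predictor of ventilator-free days, although it has no baseline value and its window closes at the event that largely sets that outcome

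*Combined protocol and SAP*

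**What the plan says.** Section 6.2 tests the primary outcome with an unadjusted two-sided t-test. It then adds: "As secondary analysis, the associations between the primary outcome and exposures and demographic variables will be further analyzed using linear regression models". The secondary outcomes get linear or logistic models "using demographic and exposure variables as predictors". No exposure is excepted, no time point is given, and the section does not say whether treatment arm is in these models. It also states "Missing values will be ignored" and "All tests will be 2-sided, and p-values < 0.05 will be considered significant".

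The table in Section 5.2 lists 12 exposures. Eleven are marked for collection at baseline and daily. The twelfth, Fluid Balance, is marked daily only and is measured as "Net fluid balance prior to extubation". The table does not say when the window opens, or whether the value is a total, a last-day figure or a mean.

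Section 6.1 gives VFD as "defined as the number of days alive and ventilator-free by day 28". Section 5.1 provides a way off the ventilator without extubation: "Any patient who fails to be eligible for extubation or fails extubation will be eligible for tracheostomy per usual unit protocol".

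**The concern.** For the other 11 exposures a reader can assume that the baseline value is meant. For fluid balance there is none, so the predictor must be post-randomisation, and it is observed up to the event that largely fixes VFD. Two problems can follow.

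- **Duration inside the predictor.** A net total sums more days in patients ventilated longer. It is then correlated with VFD and length of stay by construction, with a sign set by the average daily balance. If arm is also in the model, the total absorbs part of the arm effect.
- **Loss of patients.** Someone who dies on the ventilator, or has a tracheostomy without a prior extubation, has no value before extubation if the definition is read literally. Ignoring missing values then removes that patient from any model containing the predictor, although VFD and tracheostomy status are known.

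At stake is the reporting of predictors. Time on the ventilator could be presented as a significant fluid effect, or predictors could be reported from a set that omits the worst courses.

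**Working it through.** **The plan's own figures.** Section 6.3 opens: "With a mean duration of mechanical ventilation of 7 days with a standard deviation of 2.9 days". Control VFD is 28 − 7 = 21. With SD 2.9, 80% power and two-sided 0.05, a t-test calculation gives 15.7 (so 16) per group for 3 days and 34.0 (so 34) per group for 2 days. Then 68/0.9 = 75.6, so 76. All reproduce, and none is disputed here.

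**Inputs.** From the documents: mean duration 7 days, SD 2.9, n = 76. Assumed, because the documents give no fluid figures: average daily net balance m = 0.25 to 1.0 L, day-to-day SD s = 1 to 2 L, between-patient SD b = 0 to 1.0 L. Daily balance is unrelated to weaning, all patients are extubated, and VFD = 28 − d.

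**Step 1: correlation of a net total C with VFD.** Cov(C, d) = m·2.9². Var(C) = (m·2.9)² + 7s² + b²(7² + 2.9²), where 7² + 2.9² = 57.41. Hence

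r = −m·2.9 / √[(m·2.9)² + 7s² + 57.41b²]

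- m 0.5, s 1.5, b 0: −1.45/√(2.10 + 15.75) = −0.34
- the same with b 0.5: −1.45/√(17.85 + 14.35) = −0.26
- the same with b 1.0: −1.45/√(17.85 + 57.41) = −0.17
- m 0.25, s 2, b 0.5: −0.725/√(0.53 + 28 + 14.35) = −0.11
- m 1, s 1, b 0: −2.9/√(8.41 + 7) = −0.74
- m −0.5, s 1.5, b 0: +0.34

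**Step 2: how often p < 0.05.** Simulated trials of 76, with duration gamma or normal, rounded to whole days from 1 to 28. Ranges cover both shapes and repeat runs.

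| Predictor and setting | Share with p < 0.05 (nominal 5%) |
|---|---|
| Total, m 0.5, s 1.5, b 0 | 84% to 87% |
| Same, b 0.5 | 59% to 62% |
| Same, b 1.0 | 31% to 38% |
| Total, weakest steady gain (m 0.25, s 2, b 0.5) | 15% to 22% |
| Total, strongest (m 1, s 1, b 0) | 100% |
| Total, average balance 0 | 6% to 9% |
| Total, +1 L/day for 3 days, then 0 | 7% to 9% |
| Last-day value | 4% to 6% |
| Per-day mean | 4% to 12% |

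For ICU stay (ventilator days plus an assumed further 3 days on average), the total at m 0.5, s 1.5, b 0 gives 66%.

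**Step 3: arm effect, if arm is in the model.** With 38 per arm, a true 2-day effect, s = 1 L and b = 0, the arm coefficient is multiplied by about 1 − ρ², where ρ² = (m·2.9)²/[(m·2.9)² + 6s²] and 6 is the mean duration over arms with 7 and 5 days. Without fluid balance the simulated effect is about 1.9 VFD (just under 2 because short durations are truncated), with power about 0.85.

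- m 0.25: 1 − 0.53/6.53 = 0.92; simulated 1.8 VFD, power 0.79
- m 0.5: 1 − 2.10/8.10 = 0.74; simulated 1.5 VFD, power 0.72
- m 1.0: 1 − 8.41/14.41 = 0.42; simulated 0.8 VFD, power 0.47

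With s = 1.5 L the simulated effect runs from 1.9 down to 1.2 VFD. With a last-day value unrelated to duration it does not move.

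**Step 4: patients lost.** The documents give no share of patients never extubated. If it were 10% to 40% (assumed), 76 × 0.9 = 68 down to 76 × 0.6 = 46 would remain. What this does to other coefficients depends on how each predictor acts, which the documents do not give.

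**The case against.** Section 6.2 never names fluid balance. It enters through the class word for exposures, and the only covariates listed anywhere (Synopsis: BMI, abdominal girth, Ptp) leave it out. The row is marked daily, not at completion, and net can mean intake minus output on one day. On that reading the first problem largely goes. The phrase about extubation may mean only days while intubated, in which case never-extubated patients do have values. If exposures are modelled one at a time, no other coefficient loses patients. The VFD regression is already called a secondary analysis of associations.

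Most of this stands, and it limits the point. It does not remove it: the text permits the total, excludes no exposure, and applies p < 0.05 to every test. The size is also fragile. More between-patient variation or an early end to the gain brings the rate down sharply, and a gain followed by net loss reverses the sign.

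Three stronger inferences are tempting and unsupported:

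- **That the treatment comparison is compromised.** The primary t-test and the unadjusted comparisons contain no covariates, the Synopsis regression does not use fluid balance, and 6.2 does not say that arm is in the exposure models.
- **That dropping never-extubated patients wipes out real predictors.** A simulated slope of zero among extubated patients appears only if the predictor is built to act solely on the chance of extubation. If it also shifts duration by 1 day per SD, the slope is about −1.0. Setting VFD to 0 for all these patients also fits poorly, since Section 5.1 lets tracheostomy patients be liberated.
- **That every secondary outcome is affected.** For reintubation within 72 hours, a balance before extubation properly precedes the outcome.

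**Conclusion.** The concern holds as a minor one, confined to secondary models. As a predictor of VFD, length of stay or tracheostomy, fluid balance can only be post-randomisation, with a window that closes at extubation. If it is analysed as a net total, spurious significance ranges from roughly 15% to 100% under assumed steady gains of 0.25 to 1.0 L/day with between-patient SD up to 0.5 L. It is 31% to 38% at 0.5 L/day with between-patient SD 1.0 L, and close to nominal if average balance is zero or the gain ends early. A last-day value or per-day mean largely avoids it. Attenuation of the arm effect, to between 1.8 and 0.8 VFD, arises only if arm is in the model and a total is used.

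The loss of never-extubated patients follows from a literal reading of 5.2 together with the missing-data rule, and its effect on estimates cannot be sized. All fluid rates are assumptions, so neither size nor direction is established for this trial.

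**What to change.** In Section 6.2, exclude fluid balance from the predictors of VFD, ICU stay, hospital stay and tracheostomy, or replace it with a value fixed before randomisation. Describe post-randomisation balance by arm as a mean per ventilator day. State that never-extubated patients stay in those models, and report the number analysed in each. The reintubation model can keep the variable.

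The cost is a few sentences. Exclusion needs no new data; a pre-randomisation value needs one added EMR field. The primary test, sample size and follow-up do not change. The trial gives up a model-based association between fluid balance and VFD, which could still be shown as an exploratory per-day description.
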